17.5 MTD and RPTD definition

The MTD will be the final recommended dose after the trial has completed recruitment using all data accumulated in the trial. The MTD will constitute the recommended phase II dose (RPTD).

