3.3 Sample Size

The sample size will be 20 evaluable patients. Evaluable patients are patients enrolled in the study who received at least one dose of atovaquone.

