6. ANALYSIS

6.1 Outcome Definitions

Primary outcome

To determine the maximum tolerated dose (MTD), and therefore recommended phase II dose (RPTD), of atovaquone when combined with radical concurrent chemoradiotherapy

The outcome is the occurrence (yes/no) of a DLT within the DLT assessment period. For patients without a DLT, time observed within the DLT assessment period will also be taken into account in the analysis. The total i.e. maximum duration of the DLT assessment period for each patient is the length of the atovaquone run-in period (1-3 weeks) which will be pre-specified before the patient starts treatment, plus the length of CRT treatment (6.5 weeks= 45 days) plus follow-up duration (12 weeks = 84 days). At final analysis, patients without a DLT will have completed the DLT period unless they withdrew early. The MTD will be the dose level with posterior mean DLT rate closest to the target toxicity level of 48% when the dose-toxicity model is updated for the final analysis.

For the definition of a DLT, see Appendix 4.

Secondary outcomes

To assess the safety and toxicity profile of atovaquone in combination with radical concurrent chemotherapy

Adverse events from the first dose of atovaquone to six months post completion of CRT will be presented (see Appendix 3).

To confirm feasibility of measuring hypoxia metagene signature using 3'RNA-Seq in diagnostic NSCLC samples

To assess agreement of FMISO PET-CT with plasma miR-210 level and tumour hypoxia gene expression pretreatment with atovaquone

Hypoxia assessed using the baseline FMISO PET-CT scan will be measured using tumour to blood ratio (TBRvolume) (ml).

Plasma miR-210 level will be derived from the baseline blood sample.

Baseline is at week -2/-3 prior to receiving the first dose of atovaquone.

To assess agreement in changes in FMISO PET-CT and plasma miR-210 level following two weeks (+/- 7 days) of atovaquone

Change in FMISO PET-CT will be the % change between TBRvolume (ml) derived from the baseline and pre-CRT scans.

Change in plasma miR-210 level will be the % change between miR-210 level derived from the baseline and pre-CRT blood samples.

Baseline is at week -2/-3 prior to receiving the first dose of atovaquone and pre-CRT is at week -1 (two weeks (+/- 7 days) after starting atovaquone and prior to receiving any CRT.

To assess the tumour response rate at three months following treatment

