6.2 Analysis Methods

Primary analysis

To determine the maximum tolerated dose (MTD), and therefore recommended phase II dose (RPTD), of atovaquone when combined with radical concurrent chemoradiotherapy

All trial patients who received at least one dose of atovaquone will be included in the primary analysis. The same analysis is used during dose escalation as for the final analysis.

The analysis will follow the TiTE-CRM. A two-parameter logistic model will be used to model the relationship between dose and toxicity i.e. the dose toxicity curve (DTC). Dose recommendations following the first two evaluable patients will be made using all current toxicity data as follows:

- Data for patients who have completed the DLT assessment period or experienced a DLT will contribute full information to this model.
- Data for patients who have not completed the DLT assessment period will contribute partial information to the model, weighted proportionally to the observed portion of their time window, and treating them as not experiencing a dose limiting toxicity. The weight function is defined in the equation below as w_i.

There are 4 atovaquone doses which are coded x = 1:4. Assuming dose 1 is the reference dose, d^* , we have treated J patients with dose x_j , j = 1, ..., J, then we model the probability of a DLT occurring using the weighted likelihood given by

$$L(\theta) = \prod_{j=1}^{J} \left[\theta_{x_j} * w_j \right]^{y_j} \left[(1 - \theta_{x_j}) * w_j \right]^{1 - y_j}$$

where

 $y_{j} = \begin{cases} 1 \text{ if dlt occured} \\ 0 \text{ if no DLT} \end{cases}$ $g\left(\theta_{x_{j}}\right) = logit\left(\theta_{x_{j}}\right) = log(\alpha) + \beta log\left(\frac{x_{j}}{d^{*}}\right) \text{ this is the unweighted two-parameter logistic model}$ $w_{j} = \begin{cases} 1 \text{ if } y_{j} = 1 \\ \min\left(1, \frac{u_{j}}{T_{i}}\right) \text{ if } y_{j} = 0 \end{cases}$

 u_j = time patient j has been followed for and T_j = total DLT window for patient j = pre-specified run-in time + 45 days + 84 days (note: as patients are followed up in the trial beyond the DLT observation period, u_j can exceed T_j in which case the weight for patient j in the model will still be 1).

Further detail on the chosen prior distributions for the parameters and simulation results is described in Appendix 1.

See Neuenschwander, Branson and Gsponer (2008) and Cheung YK and Chappell R (2000) for descriptions of the model

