SAP Version No: V1.0 Date: 17Jun2021 SAP Author: [name] OCTRU-OST-001_V3.0_16Feb2018 Effective Date 23Feb2018

Dose-escalation rules

At each analysis the dose recommended by the toxicity model will be the dose with posterior mean DLT rate closest to the target toxicity level of 48%, subject to no dose skipping. However in order to escalate to the next dose, there must also be at least one patient on the previous highest dose fulfilling the following criteria:

- Completed ≥1 full cycle of CRT (i.e. at least three weeks of RT)
- Received ≥50% the specified dose of cisplatin
- Taken ≥75% their allocated dose of atovaquone
- Not experienced a DLT

There is no restriction on dose de-escalation.

Early stopping

At each analysis, the TMG will be recommended to stop the trial early for safety if there is greater than 70% probability that the DLT rate at the lowest dose (dose 1) exceeds the target toxicity level of 48% i.e. if P(risk of DLT>0.48 | dose = 1, current data) > 0.7, which would suggest the lowest dose is too toxic.

Definition of MTD

The MTD will be the final recommended dose after the trial has completed recruitment and all participants had completed the DLT window (or had a DLT/withdrawn) using all data accumulated in the trial. The MTD will constitute the RPTD.

If the trial stops early for toxicity, the MTD will be assumed to be lower than dose 1 and the RPTD will not be established.

Secondary and tertiary analyses

There will be no formal analysis of the secondary or tertiary objectives. See template in Appendix 3 for tables and figures that will be presented.

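### The final MTD rule is not limited to dose levels given in the trial, so it can name as RPTD a level that no patient received

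*SAP*

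**What the plan says.** SAP 6.1 (primary outcome): "The MTD will be the dose level with posterior mean DLT rate closest to the target toxicity level of 48" per cent, taken when the model is updated for the final analysis. No condition is set on how many patients received that level.

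SAP 6.2 (Definition of MTD): "The MTD will be the final recommended dose after the trial has completed recruitment and all participants had completed the DLT window". Protocol 17.5 gives the same definition in shorter form. Both documents then make the MTD the RPTD.

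SAP 6.2 also says: "The same analysis is used during dose escalation as for the final analysis". At each analysis the recommended dose is the one with posterior mean "closest to the target toxicity level of 48%, subject to no dose skipping". To escalate, "there must also be at least one patient on the previous highest dose fulfilling the following criteria": at least one full cycle of CRT, at least half the cisplatin dose, at least three quarters of the atovaquone dose, and no DLT. Protocol 17.3 sets the same conditions.

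SAP 3.3 fixes the size of the trial: "The sample size will be 20 evaluable patients". No minimum number per dose level is given.

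**The concern.** During the trial it is sound for the model to recommend a level that nobody has had. The next patient is given that level, and the data then confirm or correct the model. At the final analysis there is no next patient. The same calculation, read under the same rule, turns a recommendation to explore into a declared MTD and RPTD.

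The two limits in SAP 6.2 do not prevent this. No-skipping allows one step above the highest level given, and the escalation criteria ask for one suitable patient on that highest level. Neither asks for anything at the level being named. SAP 6.1 does not repeat even those limits.

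At an untried level the posterior mean comes from the prior and the shape of the logistic curve. Protocol 1.2 says that an exacerbation of CRT side effects by atovaquone cannot be conclusively ruled out, and Protocol 1.4 makes further trials depend on the RPTD. A later trial could therefore start at a level described as the MTD with CRT, with no patient having received the combination at that level.

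**Working it through.** **What can be reproduced.** The documents give no formula for 20 patients. The priors and operating characteristics are in SAP Appendix 1, a separate document. Only the accrual arithmetic can be checked: 20 patients / 1 per month = 20 months, which agrees with Protocol 17.4.

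**Model (SAP 6.2).** "There are 4 atovaquone doses which are coded x = 1:4", with dose 1 as reference, so logit(theta_x) = log(alpha) + beta·log(x). For patients with a DLT or a complete window the weight is 1, and the likelihood is the product over levels of theta_x^DLTs × (1 − theta_x)^(n − DLTs).

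**Assumed priors** (mean, SD):
- A: log alpha ~ N(logit 0.30, 1.5), log beta ~ N(0, 0.7)
- B: log alpha ~ N(logit 0.25, 2), log beta ~ N(0, 1)
- C: log alpha ~ N(logit 0.40, 1), log beta ~ N(−1, 0.5)

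**Example 1: an untried level is named.** This is a simulated trial that obeyed the rules: 6/8/6/0 patients at doses 1 to 4, with 2/3/2/0 DLTs. Posterior means by numerical integration on a grid:

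| Prior | Dose 1 | Dose 2 | Dose 3 | Dose 4 | Distance from 0.48, dose 3 | Distance from 0.48, dose 4 |
|---|---|---|---|---|---|---|
| A | 0.256 | 0.367 | 0.443 | 0.497 | 0.037 | 0.017 |
| B | 0.262 | 0.359 | 0.426 | 0.474 | 0.054 | 0.006 |
| C | 0.318 | 0.376 | 0.412 | 0.438 | 0.068 | 0.042 |

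Dose 4 is closest under all three priors, and nobody received it. It is one step above dose 3, so no-skipping allows it. The posterior probability that its DLT rate exceeds 48% is between 35% and 54% across the three priors.

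**Example 2: the literal wordings differ.** Patients 15/5/0/0 with 6/0/0/0 DLTs, prior A, gives means 0.278/0.381/0.447/0.493. SAP 6.1 on its own selects dose 4 (distance 0.013), two levels above anything given. With no-skipping from SAP 6.2 the choice is dose 3 (distance 0.033), which is also untried.

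**How often.** The stated rules were simulated:
- 20 patients, one per month
- first two patients at dose 1, with 12 weeks of data before escalation
- one qualifying patient needed to escalate, and no skipping
- safety stop at probability 0.7
- DLT window: run-in of 7 to 21 days + 45 + 84 = 136 to 150 days; 143 used

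Assumed: the three priors, seven toxicity scenarios, uniform DLT times, the standard weighting (1 − w·theta) for DLT-free patients, and no TMG override. SAP 6.2 prints the weight as a multiplier of (1 − theta); this barely matters at the final analysis, where nearly all weights are 1. There were 500 trials per combination of prior and scenario.

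- MTD at a level given to nobody, with no-skipping and the escalation criteria applied at the end: about 0.2-5% of trials.
- The same on the literal SAP 6.1 wording: about 0.2-5%.

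At 5%, the simulation standard error is √(0.05 × 0.95 / 500) ≈ 1 percentage point.

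**Effect of restricting the final choice to levels with at least one treated patient** (priors A and C, four scenarios, 400 trials each). Untried MTDs fall to 0%. The selected dose changes in this share of trials:

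| True DLT rates, doses 1-4 | Prior A | Prior C |
|---|---|---|
| 0.10, 0.15, 0.20, 0.25 | 0.25% | 0% |
| 0.25, 0.33, 0.40, 0.48 | 2.5% | 1.25% |
| 0.25, 0.37, 0.48, 0.60 | 3.0% | 0.75% |
| 0.35, 0.48, 0.60, 0.70 | 1.75% | 1.75% |

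**The case against.** **The rates are not this trial's.** Protocol 17.2 says the priors were calibrated, and Protocol 17.3 reports 1000 simulations per scenario. The real priors could make the event rarer or more frequent. This stands: the percentages show scale only. The gap in the wording does not depend on them.

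**Other checks exist.** Protocol 17.3 and SAP 3.4 have the TMG review every model recommendation, and the Safety Review Committee can review escalation decisions. The Protocol Decision Point Plan and TMG charter might hold a limit. But the review is described for allocating doses to patients; no check is written for the final MTD, and the MTD definitions refer to no such limit. SAP 3.4 also lets the TMG choose a lower dose than the model, which can leave upper levels untried while the final rule still reads the model alone.

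**A reader might infer that an MTD resting on one or two patients is an equal fault.** The documents do not support that. Protocol 17.1 describes a model-based method with monotone toxicity that uses all accumulated data. Thin data at the chosen level, supported by the fitted curve, is ordinary behaviour for such a design. A minimum number per level would be a preference; what is needed is that the number is visible.

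**A reader might also infer that SAP 6.1 and 6.2 are two conflicting rules.** Read together they are mostly consistent: 6.1 states the outcome, and 6.2 applies no-skipping at each analysis and uses the same analysis at the end. They can part in a dataset such as Example 2, but the simulated rates are almost the same under either reading. This is a matter of aligning wording.

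**Conclusion.** The point holds as a missing safeguard on the primary endpoint; it is not an arithmetic error. Followed as written, SAP 6.1, SAP 6.2 and Protocol 17.5 can name as RPTD a level that nobody received: one above the highest given or, on the literal wording of SAP 6.1 alone, more than one above. That this is possible follows from the text, and under all three assumed priors Example 1 names the untried dose 4. It is uncommon, and the frequency found rests on assumed priors, assumed toxicity curves and no TMG override, so it should not be quoted as a property of this design. The change is worth making because it is cheap and protects the one result that later trials will use.

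**What to change.** State one rule in SAP 6.1, SAP 6.2 and Protocol 17.5, for example:

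> At the final analysis the MTD is the dose level with posterior mean DLT rate closest to 48% among levels at which at least one patient in the primary analysis population was treated. If the level closest under the model is untried, the closest tried level is reported, with a statement that escalation was incomplete.

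Eligibility should rest on having been treated, not on having completed the DLT window. A stricter condition could exclude a level whose patients all withdrew without a DLT, although SAP 4.2 keeps them in the primary population and SAP 6.2 counts them by partial weight.

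Report the number of patients, the number of DLTs and the posterior interval at the named MTD beside it, so that an MTD resting on one or two patients can be seen as such.

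Cost: one sentence in the SAP's two places and a matching protocol clarification. A few trials would end with escalation reported as incomplete instead of with a higher named dose.

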6.2 Analysis Methods

Primary analysis

To determine the maximum tolerated dose (MTD), and therefore recommended phase II dose (RPTD), of atovaquone when combined with radical concurrent chemoradiotherapy

All trial patients who received at least one dose of atovaquone will be included in the primary analysis. The same analysis is used during dose escalation as for the final analysis.

The analysis will follow the TiTE-CRM. A two-parameter logistic model will be used to model the relationship between dose and toxicity i.e. the dose toxicity curve (DTC). Dose recommendations following the first two evaluable patients will be made using all current toxicity data as follows:

- Data for patients who have completed the DLT assessment period or experienced a DLT will contribute full information to this model.
- Data for patients who have not completed the DLT assessment period will contribute partial information to the model, weighted proportionally to the observed portion of their time window, and treating them as not experiencing a dose limiting toxicity. The weight function is defined in the equation below as w_i.

There are 4 atovaquone doses which are coded x = 1:4. Assuming dose 1 is the reference dose, d^* , we have treated J patients with dose x_j , j = 1, ..., J, then we model the probability of a DLT occurring using the weighted likelihood given by

$$L(\theta) = \prod_{j=1}^{J} \left[\theta_{x_j} * w_j \right]^{y_j} \left[(1 - \theta_{x_j}) * w_j \right]^{1 - y_j}$$

where

 $y_{j} = \begin{cases} 1 \text{ if dlt occured} \\ 0 \text{ if no DLT} \end{cases}$ $g\left(\theta_{x_{j}}\right) = logit\left(\theta_{x_{j}}\right) = log(\alpha) + \beta log\left(\frac{x_{j}}{d^{*}}\right) \text{ this is the unweighted two-parameter logistic model}$ $w_{j} = \begin{cases} 1 \text{ if } y_{j} = 1 \\ \min\left(1, \frac{u_{j}}{T_{i}}\right) \text{ if } y_{j} = 0 \end{cases}$

 u_j = time patient j has been followed for and T_j = total DLT window for patient j = pre-specified run-in time + 45 days + 84 days (note: as patients are followed up in the trial beyond the DLT observation period, u_j can exceed T_j in which case the weight for patient j in the model will still be 1).

Further detail on the chosen prior distributions for the parameters and simulation results is described in Appendix 1.

See Neuenschwander, Branson and Gsponer (2008) and Cheung YK and Chappell R (2000) for descriptions of the model

SAP Version No: V1.0 Date: 17Jun2021 SAP Author: [name] OCTRU-OST-001_V3.0_16Feb2018 Effective Date 23Feb2018

Dose-escalation rules

At each analysis the dose recommended by the toxicity model will be the dose with posterior mean DLT rate closest to the target toxicity level of 48%, subject to no dose skipping. However in order to escalate to the next dose, there must also be at least one patient on the previous highest dose fulfilling the following criteria:

- Completed ≥1 full cycle of CRT (i.e. at least three weeks of RT)
- Received ≥50% the specified dose of cisplatin
- Taken ≥75% their allocated dose of atovaquone
- Not experienced a DLT

There is no restriction on dose de-escalation.

Early stopping

At each analysis, the TMG will be recommended to stop the trial early for safety if there is greater than 70% probability that the DLT rate at the lowest dose (dose 1) exceeds the target toxicity level of 48% i.e. if P(risk of DLT>0.48 | dose = 1, current data) > 0.7, which would suggest the lowest dose is too toxic.

Definition of MTD

The MTD will be the final recommended dose after the trial has completed recruitment and all participants had completed the DLT window (or had a DLT/withdrawn) using all data accumulated in the trial. The MTD will constitute the RPTD.

If the trial stops early for toxicity, the MTD will be assumed to be lower than dose 1 and the RPTD will not be established.

Secondary and tertiary analyses

There will be no formal analysis of the secondary or tertiary objectives. See template in Appendix 3 for tables and figures that will be presented.

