6 EARLY PATIENT WITHDRAWAL

Treatment Withdrawal

During the course of the trial, a patient may withdraw early from treatment. This may happen for a number of reasons, including:

- Unacceptable toxicity
- AE/SAEs requiring discontinuation
- Loss to follow-up
- Significant protocol deviation or inability to comply with trial procedures
- Clinical decision
- Patient decision

When the patient stops treatment, the 'End of Treatment' Form needs to be completed, and any other relevant CRFs (example SAE Form) and the Trial Office notified within 24 hours. The reason for withdrawing from treatment early, should be clearly documented in the medical records.

Patients who have stopped treatment early should continue to be invited to all follow-up visits and assessments, unless patient consent for follow-up is withdrawn.

Participants have the option to consent to NHS Digital follow-up. This will entail completion of a separate tracing sheet which will contain the participant's name and NHS number, and will therefore be kept securely by the Trial Office. This will enable future ethically-approved trials to trace participants' outcome data for long term follow up.

Consent Withdrawal

Consent withdrawal means that a patient has expressed a wish to withdraw from the study altogether. Under these circumstances, the site needs to document all relevant discussions in the patient notes and notify the Trial Office, which will allow the office to mark all future CRFs as not applicable.

Data and samples collected prior to participant consent withdrawal will be used for trial analysis. Participants who initially consented to be registered with NHS Digital or equivalent will remain on the system so that important long term follow up data can be requested from NHS Digital, unless the patient specifically requests that permission is withdrawn to do so.

Under these conditions, Investigators are still responsible for following up any SAEs until resolution.

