8.6 Dose modification

Atovaquone

If chemotherapy is reduced or stopped, atovaquone should be continued.

If RT is suspended for less than seven consecutive days for reasons other than toxicity, atovaquone treatment can also be suspended (at the clinician's discretion), but restarted with RT.

If RT is interrupted for less than seven days due to toxicity, atovaquone should be stopped when RT is discontinued and not restarted.

Interruptions of RT of greater than seven days for toxicity reasons (related to IMPs, CRT or the combination thereof) are defined as DLTs, in which case atovaquone should be permanently discontinued.

If a patient experiences toxicity that is thought to be directly related to atovaquone treatment and not controlled by supportive medication, then atovaquone should be discontinued, rather than the dose reduced, and it should not be restarted. Investigators are encouraged to discuss such decisions to discontinue atovaquone with the CI. See section 9 for effects defined as dose limiting toxicities and reporting procedure.

Single agent atovaquone treatment is not usually associated with significant side effects and as this drug has been prescribed for many years it has a well-established toxicity profile. It is not expected that addition of atovaquone to CRT will increase side effects, however this may occur and will be reported as part of the safety and DLT assessment, if applicable.

Cisplatin and vinorelbine

The following dose modification schedule is recommended for haematological and biochemical abnormalities on chemotherapy. As each patient's clinical circumstances are unique, these are intended as a guide only.

ANC (x10 ⁹ /L)		Platelets (x10 ⁹ /L)	Chemotherapy dose
≥1.5	And	≥100	100%
<1.5	Or	<100	Delay one week and reassess
<1.0	-	_	Delay one week, give additional 5 days antibiotics and reassess

Haematology for cisplatin:

Haematology for vinorelbine:

ANC (x10 ⁹ /L)		Platelets (x10 ⁹ /L)	Chemotherapy dose
≥1.5	And	≥100	100%
<1.5	And	<100	Omit
Febrile neutropenia	Or	Grade ≥4 haematological toxicity	75%

Renal dysfunction for cisplatin:

Creatinine clearance (mL/min)	Chemotherapy dose
>60	100%
40-60	62.5%
<40	Discontinue

Oto- and neurotoxicity for cisplatin:

Ototoxicity or neurotoxicity	Chemotherapy dose
< Grade 3	100%
≥ Grade 3	Discontinue

Hepatic dysfunction for vinorelbine:

ALT		Total bilirubin	Chemotherapy dose
<5 x ULN	And	<2 x ULN	100%
>5 x ULN	And/or	>2 x ULN	70%

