17 STATISTICAL CONSIDERATIONS

17.1 Study design

This is a phase I, single arm, open label, two-centre study. The primary objective is to identify the MTD, and thus RPTD, of atovaquone when combined with concurrent CRT in NSCLC using a Bayesian TiTE-CRM design.

The CRM is a model-based method for finding the maximum tolerated dose (MTD) under the defining monotonicity assumption which posits that toxicity increases monotonically with increasing dose, and that efficacy also increases with increasing dose. The objective is to find the dose with a probability of experiencing a Dose Limiting Toxicity (DLT) close to a pre-specified target toxicity level. The TiTE-CRM is a modified version of the CRM that allows late-onset toxicities to be accounted for without fully observing a patient before recruiting the next and is therefore particularly advantageous for radiotherapy trials where toxicities are often observed later than in studies using systemic therapy alone. A major advantage of the TiTE-CRM is the fact that it uses all current accumulated information to decide which dose to assign the next patient. A further advantage of this design is that it will be able to include partial information on patients who could not be formally evaluated for DLTs due to withdrawal, treatment discontinuation or death, that is unrelated to treatment within the DLT assessment period (from week-2/-3 to three months post-CRT). In addition, the method results in shorter study duration as it is not necessary for a patient to be observed for the full observation period before recruiting the next patient, and also more patients are treated close to the MTD.

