17.2 The TiTE-CRM model

A two-parameter Bayesian logistic model with weak priors will be used. The priors are calibrated to ensure the model provides sensible recommendations early in the trial. With this model we can obtain a distribution for the probability of DLT rate given a specific dose d based on all available data. This is a posterior probability distribution for dose d. We write P(T>0.48 | Data, dose = d) to mean the posterior probability that the DLT rate is greater than 48% on dose d, given the data observed so far.

At each dose decision (to assign a dose to the next patient), data for patients who have completed the DLT assessment period or experienced a DLT will contribute full information to this model. Only partial information is known for patients who are currently on trial, within the DLT assessment period, or have stopped treatment in the DLT assessment period for reasons other than a DLT. This partial information contributes to the model, weighted proportionally to the observed portion of their toxicity time window and treating them as not experiencing a DLT.

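### SAP 6.2 weights by time followed alone, so a DLT-free patient who stops before or early in CRT can count as a full observation of the combination

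*SAP*

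**What the plan says.** SAP 6.2 sorts patients into two groups. Full information: "Data for patients who have completed the DLT assessment period or experienced a DLT will contribute full information to this model". Partial information: "Data for patients who have not completed the DLT assessment period will contribute partial information to the model". For a patient without a DLT the weight is w_j = min(1, u_j/T_j). Here u_j is defined as "time patient j has been followed for", and T_j is the pre-specified run-in plus 45 plus 84 days. Neither term depends on how much atovaquone or CRT was given. One dose is enough to enter the primary analysis and to count towards the 20 (SAP 3.3: "Evaluable patients are patients enrolled in the study who received at least one dose of atovaquone").

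Protocol 17.2 names one more partial-information group: patients who "have stopped treatment in the DLT assessment period for reasons other than a DLT". Protocol 17.1 lists as an advantage of the design that it can use "partial information on patients who could not be formally evaluated for DLTs due to withdrawal, treatment discontinuation or death". SAP 6.2 does not mention this group.

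Two other protocol sections bear on the point:
- Section 6 keeps stoppers under observation: "Patients who have stopped treatment early should continue to be invited to all follow-up visits and assessments".
- Section 8.6 gives routes to permanent discontinuation that need not meet a DLT criterion. One is: "If RT is interrupted for less than seven days due to toxicity, atovaquone should be stopped when RT is discontinued and not restarted". The other is atovaquone-related toxicity that supportive medication does not control.

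SAP 4.2 and 6.4 add a sensitivity analysis, at each interim and at the end, limited to patients with more than 75% of prescribed atovaquone plus all patients with a DLT. Escalation also requires at least one DLT-free patient on the previous highest dose with at least 75% of allocated atovaquone.

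**The concern.** The primary objective is the MTD of atovaquone given with CRT. Under SAP 6.2, a patient who takes a single dose, never starts CRT, attends follow-up and has no DLT ends as a complete DLT-free observation of the combination at the assigned dose. A patient who stops early in CRT was partly exposed but gets the same full weight. If atovaquone adds toxicity, such follow-up pulls the estimated DLT rate at that dose down, which favours escalation and a higher MTD. Some of these stops would be caused by toxicity short of a DLT, so they may be more common at the doses where accuracy matters most.

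**Working it through.** **Inputs from the documents.** Run-in 7 to 21 days; CRT 45 days; post-CRT window 84 days (SAP 6.1, 6.2). Planned atovaquone 59 days (Protocol 8.2). Target DLT rate 48%. Sample size 20.

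**1. Reproduce the plan's figures.** Atovaquone with a 14-day run-in: 14 + 45 = 59 days, as Protocol 8.2 states. T_j = 7 + 45 + 84 = 136, 14 + 45 + 84 = 143, or 21 + 45 + 84 = 150 days.

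**2. Weight of a DLT-free stopper followed to T_j = 143.**

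| Atovaquone stopped | SAP weight | Cut at stop day | Share of planned atovaquone |
|---|---|---|---|
| Day 14, before CRT | 1.00 | 14/143 = 0.10 | 14/59 = 0.24 |
| Day 35, three weeks into CRT | 1.00 | 35/143 = 0.24 | 35/59 = 0.59 |
| Day 54, near the end of CRT | 1.00 | 54/143 = 0.38 | 54/59 = 0.92 |

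Across run-ins of 7 to 21 days, the cut weight is 0.05 to 0.14 for a stop at the end of the run-in, and 0.21 to 0.28 for a stop three weeks into CRT.

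**3. Direction.** Let a share s of patients at a dose stop early. Apparent rate = (1 − s) × p1 + s × p0, where p1 is the rate when fully exposed and p0 the rate in stoppers. All values here are assumptions. With p1 = 0.55 and p0 = 0.25, s = 0.1, 0.2, 0.3 gives 0.52, 0.49, 0.46. With p0 = 0.10 it gives 0.505, 0.46, 0.415. If p0 = p1 there is no bias.

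**4. Effect on the recommendation.** The SAP's two-parameter logistic model was fitted with doses coded 1 to 4 and the usual TiTE-CRM likelihood, (wθ)^y (1 − wθ)^(1−y). Priors are assumed, because Appendix 1 is a separate document: log α ~ N(logit 0.25, SD 2) and log β ~ N(0, SD 1). The data sets are invented. Stoppers are DLT-free and leave at day 14, so their weight goes from 1.00 to 0.10.

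| Patients/DLTs at doses 1–4 | Stoppers | Posterior mean, dose 4 | Recommended level |
|---|---|---|---|
| A: 3/1, 4/1, 6/3, 7/3 | two at dose 4 | 0.476 → 0.543 | 4 → 3 |
| B: 3/1, 5/2, 6/3, 6/3 | one at dose 3, two at dose 4 | 0.535 → 0.650 | 3 → 2 |
| C: 2/0, 4/1, 6/2, 8/4 | two at dose 4 | 0.445 → 0.515 | 4 → 4 |

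With a tighter prior (SD 1; log β ~ N(−0.5, SD 0.7)) the dose-4 means move 0.459 → 0.512, 0.511 → 0.604 and 0.421 → 0.471, with the same level changes. Using weight 0.24 (14/59) instead of 0.10 under the first prior gives the same levels; in A the dose-4 mean is 0.537.

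**5. The printed likelihood.** SAP 6.2 prints the DLT-free term as (1 − θ) × w. There w is a constant factor and cancels from the posterior. Refitting A, B and C in that form, changing the weight changed nothing. This also contradicts the SAP's own statement that incomplete follow-up gives partial information.

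**The case against.** **The conflict may be largely verbal.** Protocol 17.2 weights all partial-information patients, stoppers included, by the share of the toxicity window observed. That is the same rule as u_j/T_j, and it too reaches 1 under full follow-up. Protocol 17.1 speaks of patients who could not be formally evaluated, for reasons unrelated to treatment. Protocol 9.1 makes anyone with one dose evaluable for DLTs, and section 18 wants non-completers followed to avoid bias. A reader might infer that the SAP breaks a protocol rule freezing the weight at the stop date. The documents contain no such rule. What stands is that the protocol puts stoppers in a separate class without saying what their weight is, and the SAP drops the class.

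**Safeguards exist.** The >75% analysis would reveal the problem: in A it gives a dose-4 mean of 0.546, close to the 0.543 from down-weighting. The TMG can override the model and may add a patient after early non-DLT drop-out (Protocol 6.1). But none of these changes the weight in the analysis that defines the MTD, and the sensitivity analysis has no decision rule. It also removes only DLT-free patients, so it pushes the estimate upward.

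**Share of window is not share of treatment.** A weight of 0.10 for a day-14 stop might be read as 10% of treatment received. A fully compliant patient is on atovaquone for only 59/143 = 41% of the window; the day-14 stopper has had 24% of planned atovaquone.

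**Frequency is unknown.** The documents report good tolerability of atovaquone alone and give no stopping rate. Toxicity that interrupts radiotherapy may itself be a DLT, and then the patient counts fully as one.

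**Conclusion.** The point holds as a gap in the primary analysis that should be closed. SAP 6.2 leaves out a class of patients that Protocol 17.1 and 17.2 single out, and as written it can give full DLT-free weight to follow-up with little or no exposure to the combination. The downward bias depends on two conditions: that atovaquone adds toxicity, and that DLT-free early stoppers occur.

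On illustrative data, two or three pre-CRT stoppers among 20 shift the top-dose estimate by 0.05 to 0.12 and the recommendation by one level in two of three data sets. That shows sensitivity and is not a forecast, since the priors and data are assumed. Stops during CRT would matter less.

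A reader might go further and infer that the MTD will be estimated from patients who did not receive the combination, or will be too high. The documents do not support that: they give no number of stoppers, and only those who stop before CRT had none of the combination.

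**What to change.** Reconcile SAP 6.2 with Protocol 17.1 and 17.2, and state the weight for stoppers explicitly:

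- **Never starts CRT, no DLT:** weight stops accruing at the stop date. The patient stays in the safety set and is listed as not informative for the combination.
- **Stops atovaquone during CRT, no DLT:** follow-up weight multiplied by the fraction of planned atovaquone received, or full weight above the SAP's existing 75% threshold. A day-54 stopper then gets 0.92 or 1.00, where freezing at the stop date would give 0.38. The multiplier can also cover a patient who stops in the run-in and then has CRT without atovaquone.
- **DLT after stopping:** state how it is counted. Full counting is conservative. For example, with a true rate of 0.55 in everyone, 20% stoppers and weight 0.10 for DLT-free stoppers, the weighted rate is 0.55/(0.55 + 0.45 × (0.8 + 0.2 × 0.10)) = 0.55/0.919 = 0.60.
- **Likelihood:** correct the printed DLT-free term to 1 − wθ and confirm that the code uses it. Without this, no change of weight has any effect.
- **Checks:** run the rule through the existing simulations and keep the current follow-up weight as a sensitivity analysis.

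The cost is SAP wording, a small change to the weight code and some extra simulation. Protocol 6 already requires an End of Treatment form, and SAP 6.3 describes a dedicated form with key compliance data. Early stoppers contribute slightly less information, so posteriors widen a little.
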